## 10.2 SITE MONITORING

Data quality will be reviewed remotely using front end range and logic checks at the time of data entry and back-end monitoring of data using SAS reports. The site PIs at the two sites will perform random audits of up to 10% of eDCFs and verify source documents. A summary of the audits will be submitted to the IRB during annual renewal. Patient records and case report forms will be examined on a spot check basis to evaluate the accuracy of the data entered into the database and monitor for protocol compliance.

## 11 RISK ASSESSMENT

This study involves randomization to either restrictive UFNET rate, or liberal UFNET rate. Compared to not being part of the study, patients may have a higher, lower, or similar risk of adverse events.

### 11.1 RISKS OF RESTRICTIVE UFNET RATE

Restrictive UFNET rates between 0.5 to 1.5 mL/kg/h may theoretically increase the risk of fluid overload, increase dependence on ventilator as well as dependence on kidney replacement therapy by prolonging fluid overload. Myocardial edema may result in increased episodes of cardiac arrhythmias. Worsening oxygenation may result in increased use of rescue procedures. However, UFNET rates used in the restrictive group are also frequently used in clinical practice and our observational studies showed a lower risk of cardiac arrhythmias than liberal UFNET rates.

### 11.2 RISKS OF LIBERAL UFNET RATE

Liberal UFNET rates between 2.0-5.0 mL/kg/h may increase the risk of hypotensive episodes and cardiac arrhythmias requiring treatment similar to that encountered in current clinical practice. Ischemic kidney injury due to hypotension may result in impaired recovery of

kidney function and longer dependence on KRT. The UFNET rates in liberal group is also widely used in clinical practice.

### 11.3 RISK OF ADVERSE EVENTS

It is possible that one treatment arm may lead to more adverse events, which will be monitored during the study. However, being a feasibility trial, the study is not powered to detect any statistically significant differences in adverse events. Many of the adverse events commonly occur during current clinical practice of fluid removal (Section 5.2.5; Table 1).

### 11.4 MINIMIZATION OF RISKS

Net ultrafiltration is currently used clinically in the treatment of patients with fluid overload during CKRT and hypotensive episodes occur in 19% to 97% of patients with a mortality rate of more than 40%. This trial will study two different approaches to fluid removal in order to minimize the risk of hypotension and ultimately to improve patient outcomes in a subsequent large multicenter randomized trial. There are several elements of study design inherent in the present protocol that ensures the minimization of risks greater than that provided during routine clinical care. Below we address the mitigation strategies used for each risk.

**Risks of the release of information:** The risk of inadvertent release of confidential information is unlikely due to the numerous protections in place. i.) All data will be collected and stored in secure files both at the participating clinical sites and at the CRISMA coordinating center. ii.) Each enrolled study participant will be assigned a study identification number, and the information to be collected and submitted to the coordinating center will not contain any personal identifiers (protected health information). iii.) We will enter all data collected by the site study coordinator using electronic data collection forms into a secure web-based study database, which will be password protected. Only the site study coordinators and the PI will have access to the password for the database. iv.) All study personnel with access to the study database will be required to complete training on the web-based data collection system and have the necessary CITI modules completed. v.) All study participant consent forms, research data, and linkage information will be stored in a secure manner with access limited to the study personnel. The linkage will be maintained by CRISMA's Biostatistics and Data Management Core's Data Manager only and is kept in a password protected location with access to no one else.

**Risk of hypotension:** i.) This protocol assesses attending physician equipoise to ensure safety before study enrollment. Subjects will not be enrolled in the study if the attending physician believes that fluid should not be removed due to severe hemodynamic instability. ii.) All patients will have continuous monitoring of blood pressure in the ICU via indwelling arterial line as per routine clinical care for early detection of hypotension. iii.) This protocol also mandates that UFNET rates do not exceed greater than 5.0 mL/kg/h in the liberal group to ensure that subjects are not exposed to high UFNET rates that are used in current clinical practice. iv.) This protocol mandates that fluid removal be completely stopped if a patient develops hemodynamic instability and provides a stepwise approach to management of

hemodynamic instability (Table 3). v.) Hypotensive episodes will be treated by slowing rate or completely stopping fluid removal. vi.) Fluid bolus and vasopressors will be administered, as needed. vii.) Fluid removal will only be restarted once the patient regains hemodynamic stability. viii.) all ICU clinicians will undergo training on study protocol and what to do when hypotension occurs.

Risk of hypertension: Hypertensive episodes related to severe fluid overload will be treated according to clinician discretion by increasing the rate of fluid removal and also with anti-hypertensive medications, as per clinician discretion.

Risk of prolonged exposure to fluid overload: i.) This protocol assesses attending physician equipoise to ensure safety before study enrollment. Subjects will not be enrolled in the study if the attending physician believes that fluid should be removed rapidly due to severe fluid overload. ii.) This protocol recommends conservative fluid management in both study arms to minimize unnecessary fluid administration (Table 4). We will recommend that all medications and infusions be double concentrated to reduce fluid volume. iii.) All patients will have daily monitoring of fluid input, output, and daily fluid balance in the ICU as part of routine clinical care. iv.) If severe fluid overload occurs, clinicians can increase the rate of fluid removal, as required, to treat fluid overload.

Risk of heart failure and pulmonary edema: If a patient develops respiratory distress due to fluid overload, this protocol provides for the option of using rapid and rescue UFNET rates, as required per clinician discretion to treat fluid overload (Table 5).

Cardiac arrhythmias: i.) Cardiac arrhythmias due to severe fluid overload will be treated by increasing the fluid removal rate as per clinician discretion. Whereas arrhythmias due to rapid fluid removal will be treated by slowing the fluid removal rate, as needed. ii.) Clinically significant cardiac arrhythmias will be treated using anti-arrhythmic agents as per clinician discretion.

Risk of increased duration of mechanical ventilation, dialysis, ICU and hospital length of stay due to fluid overload will be treated by increasing fluid removal rate, as per clinician discretion.

Risk of surgical wound edema, bowel ischemia and anastomotic break down, and ileus, abnormal liver function, delirium, poor wound healing due to fluid overload will be treated by increasing fluid removal rate as clinically indicated to treat organ edema and dysfunction per discretion of treating clinicians.

Risk of wound infections and secondary infections: Patients will be monitored for wound infections due to fluid overload. Wound infection will be treated using debridement or antibiotics as per clinician discretion.

Risk of hypophosphatemia, hypokalemia, hypocalcemia: Electrolytes will be monitored frequently as per ICU protocol. Severe hypophosphatemia, hypokalemia, and hypocalcemia will be treated by appropriate electrolyte replacement.

**Risk of arterial and venous thrombosis:** Patients will be monitored for arterial and venous thrombosis. Arterial and deep venous thrombosis will be treated with anticoagulation, as per the discretion of treating clinicians.

**Risk of anemia, hemolysis, and thrombocytopenia:** Hematology labs will be monitored daily in all patients. Clinically significant anemia, hemolysis, and thrombocytopenia will be treated with administration of blood products, as per the discretion of treating clinicians.

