### 7.4 COMMON STRATEGIES FOR ALL STUDY GROUPS

#### 7.4.1 STUDY STARTUP PROCEDURES

In both the study groups, we will use the following standardized, stepwise, startup procedures. Close oversight of study initiation will be provided by an intensive care attending and/or designee.

1. Ensure MAP  $\geq 65$  mmHg.
2. Ensure that the CKRT is operational.
3. Before starting UFNET, a study investigator or designee will determine hemodynamic appropriateness for UFNET using the following as guidelines: MAP  $\geq 65$  mmHg or SBP  $>90$  mmHg, no fluid bolus has been administered, no new vasopressor has been started, or dose of vasopressor increased in the last hour.
4. Study investigator or designee following discussion with the attending physician will ensure there are no emergency indications for fluid removal.
5. In both the arms, UFNET will be initiated within 24 hours of study enrollment.
6. In the restrictive UFNET rate arm, UFNET will be started at 0.5 mL/kg/h and increased to a maximum of 1.5 mL/kg/h. The UFNET rate can be titrated by clinicians between 0.5-1.5 mL/kg/h, as tolerated.
7. In the liberal UFNET rate arm, UFNET will be initiated at 0.5 mL/kg/h and gradually increased 0.5 mL/kg/h to a maximum of 5.0 mL/kg/h. The UFNET rate can be titrated by clinicians between 2.0-5.0 mL/kg/h, as tolerated.
8. In both the study arms, UFNET rate can be decreased or stopped at the discretion of clinicians for hypotension. Following resolution of hypotension, UFNET rate can be restarted and increased as tolerated as per the assigned treatment arm.
9. In both the study arms, at any given day and time, the UFNET rate as per study protocol can be held if the clinicians decide to use CKRT for maintaining euvoolemia (*i.e.*, no net fluid removal from patient).

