**Table 3: Interventions for managing hemodynamic instability**

1.	Completely stop $UF_{NET}$ ( i.e. , no fluid removal)
2.	Stop or reduce the dose of sedative medication infusion
3.	Stop or reduce the dose of any medication that is known to cause hypotension
4.	Administer Plasmalyte or Lactated Ringers fluid bolus of 250 mL (may repeat as needed) AND/OR Start or increase norepinephrine to maintain MAP $\geq 65$ mmHg

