#### 7.4.2.4 *Re-initiation of $UF_{NET}$ following hemodynamic instability*

Following resolution of hypotension and attending physician approval, the bedside clinician will ensure that MAP  $\geq 65$  mmHg. The  $UF_{NET}$  rate will be set at 0.5 mL/kg/h and increased as tolerated per the assigned treatment arm.

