### 4.2.1 THE BETWEEN-GROUP DIFFERENCE IN MEAN DELIVERED UFNET RATE

The primary objective is to measure a minimum of 0.52 mL/kg/h separation in the delivered patient mean UFNET rates between the restrictive and liberal UFNET rate groups. We chose between-group separation as a feasibility metric because it is a robust measure of adherence to complex protocols and has been used in ICU trials assessing the feasibility of frequently titrated interventions. Specifically, we reasoned that a larger study would not be feasible if the separation in the UFNET rates were less than 0.52 mL/kg/h. We chose 0.52 mL/kg/h as a clinically meaningful difference because our preliminary data indicated that a 0.50 mL/kg/h increase in UFNET rate is associated with increased mortality.

For between-group differences in delivered UFNET rates, we will report the patient-averaged UFNET rate with a corresponding 95% confidence interval. The patient averaged UFNET rate was the average of all hours for days where any UFNET was delivered. We will not include hours during which no fluid was removed during CKRT. We will use GLMM with a two-sided alpha of 0.05 to test the null hypothesis that the mean difference in the patient averaged delivered UFNET rate was less than 0.52 mL/kg/h after adjusting for the above prespecified variables.

We will also perform exploratory analysis in which we will examine between-group differences in peak (*i.e.*, maximum) delivered UFNET rates. We will also examine differences in longitudinal trajectories of mean delivered UFNET rate between the restrictive and liberal UFNET groups over time. We will perform subgroup analysis in which we will examine between-group differences in mean delivered UFNET rates among those with and without >10% fluid overload at enrollment; eGFR greater or less than 60mL/min/1.73m^2; duration of UFNET before enrollment (*i.e.*, greater or less than 6 hours); age  $\geq 65$  and  $< 65$  years; with and without sepsis; and baseline cardiovascular SOFA score  $\geq 3$  and  $< 3$ .

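### The protocol both requires a complete stop and allows slowing for hypotension, and the mean delivered rate counts the two responses differently

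*Protocol*

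**What the plan says.** **Response to hypotension.** Protocol 11.4, item iv: "This protocol mandates that fluid removal be completely stopped if a patient develops hemodynamic instability". Item v of the same list: "Hypotensive episodes will be treated by slowing rate or completely stopping fluid removal". Table 3 opens its steps for instability with "Completely stop". Section 7.4.1 item 8 says the "rate can be decreased or stopped at the discretion of clinicians for hypotension". Item 11 of the Trial Summary recommends withholding, as judged by bedside clinicians.

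**Restart.** Under 7.4.2.4, once MAP is at least 65 mmHg, the rate "will be set at 0.5 mL/kg/h and increased as tolerated per the assigned treatment arm".

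**Mean delivered rate.** SAP 4.2.1 says "We will not include hours during which no fluid was removed during CKRT". The sentence just before it averages over all hours of any day on which fluid was removed.

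**Protocol deviation.** Sections 5.8.1 and 10.1 and SAP 4.2.2 count a rate more than 0.5 mL/kg/h outside the assigned range for more than six consecutive hours during fluid removal, without MAP below 65 or at least 90 mmHg. Sections 5.8.1 and SAP 4.2.2 then exempt decreasing or stopping for hypotension in general terms. Section 10.1 exempts the same actions only for those MAP values.

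**The concern.** The protocol gives two instructions for the same event. If the terms described different patients there would be no conflict, but they do not. Section 7.4.2.2 defines instability by new MAP below 65, SBP below 90, a fall in SBP above 40, or a vasopressor or fluid response. SAP 5.2.2.1 defines intradialytic hypotension by essentially the same list.

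This is a safety instruction, which is reason enough to reconcile it. It also reaches the analysis. Whether a clinician stops or slows decides whether those hours enter the patient's mean rate, and between-group separation in that mean is the first feasibility criterion. Section 11.2 expects more hypotension at liberal rates, so the effect need not cancel between arms.

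**Working it through.** **1. The benchmark.** The protocol's separation criterion is 0.53 mL/kg/h (the SAP has 0.52). It reproduces as a detectable difference. The Hussey-Hughes variance with 10 ICUs, 11 periods (one baseline, ten steps; my assumption), 111 patients, SD 0.75 and ICC 0.01 gives 80.8% power at 0.53 and a detectable difference of 0.525. This point does not dispute that figure; 0.53 serves only as a yardstick.

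**2. Effect on the mean rate.** Let H be hours of treatment, h hours affected, r the usual rate and s the slowed rate.
- Stopped, zero hours dropped: mean = r.
- Slowed: mean = [(H − h)r + hs]/H.

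Assumptions, for illustration only: h = 6 and s = 0.5. H is 24, or 96 (the four-day average CKRT duration in 5.2.8). The affected share is 43% (5.2.5, Table 1).

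| Arm, usual rate | H | Mean if slowed | Patient shift | Group shift (× 0.43) |
|---|---|---|---|---|
| Liberal 2.0 | 24 | (18×2.0 + 6×0.5)/24 = 1.625 | 0.375 | 0.16 |
| Liberal 2.0 | 96 | (90×2.0 + 6×0.5)/96 = 1.906 | 0.094 | 0.04 |
| Liberal 3.0 | 24 | (18×3.0 + 6×0.5)/24 = 2.375 | 0.625 | 0.27 |
| Liberal 3.0 | 96 | (90×3.0 + 6×0.5)/96 = 2.844 | 0.156 | 0.07 |
| Restrictive 1.0 | 24 | (18×1.0 + 6×0.5)/24 = 0.875 | 0.125 | 0.05 |
| Restrictive 1.0 | 96 | (90×1.0 + 6×0.5)/96 = 0.969 | 0.031 | 0.01 |

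If both arms are affected equally, separation moves by 0.43 × (0.094 − 0.031) = 0.03 up to 0.43 × (0.625 − 0.125) = 0.215. Sections 5.1.4 and 11.4 also cite 19% to 97% of patients with hypotension; the shifts scale in proportion to the share used.

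**3. The other reading of SAP 4.2.1.** If zero hours count, a stop gives 18×2.0/24 = 1.50 for the liberal patient at 2.0 over 24 h, below the 1.625 for slowing. The direction reverses, but the two responses still score differently.

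**4. Deviation texts side by side.** Take a rate slowed for SBP below 90, or alongside a vasopressor increase, with MAP between 65 and 90. That is instability under 7.4.2.2. It is exempt under the general wording of 5.8.1 and SAP 4.2.2 but not under 10.1. A slowed hour is still during fluid removal and can count; a stopped hour cannot.

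**5. Ramps.** The liberal lower deviation limit is 2.0 − 0.5 = 1.5.
- At 0.5 the rate is 1.5 below range, and at 1.0 it is 1.0 below; both are outside tolerance.
- At 1.5 it is exactly 0.5 below, which does not count.
- With k hours per step, the out-of-limit run is 2k hours, which exceeds six only if k is above 3. At k = 2 it is 4 h (no deviation); at k = 4 it is 8 h (deviation). No step interval is stated.

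The restrictive lower limit is 0.5 − 0.5 = 0, so no positive rate can deviate low.

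**The case against.** A reader might infer more than the documents support, and the other side is right on several points.

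- **That stop and slow are scored differently across the primary outcomes.** Sections 5.8.1 and SAP 4.2.2 exempt both responses to hypotension, and recruitment is unaffected. The difference follows directly only for the mean rate; for deviation it needs the narrower wording of 10.1.
- **That following the start and restart rule creates liberal-arm deviations.** It can, but only if the first two steps together exceed six hours. A restart raised as tolerated after hypotension is arguably exempt hemodynamic titration, although MAP has by then recovered.
- **That every liberal start is at 0.5.** Section 7.2 treats patients already on fluid removal separately: raised gradually to 2.0, continued in range, or reset to 5.0. Its 70 kg example of 35 to 350 mL/h even puts 0.5 mL/kg/h inside the liberal range, against the 2.0 to 5.0 stated there.
- **That the separation could nearly halve.** Ten affected hours in one 24 h day, with usual rates of 3.0 and 1.0, give (14×3.0 + 10×0.5)/24 = 1.96 and (14×1.0 + 10×0.5)/24 = 0.79. Separation is then 1.17 instead of 2.0. That is an extreme day. Over 96 h the same ten hours give 2.74 and 0.95, a separation of 1.79. Both exceed 0.53.
- **That ICUs will divide into stoppers and slowers and bias the comparison.** Nothing shows this. All ICUs receive common training (6.2), and the ICU random effects partly absorb stable habits, though not an effect that differs by arm.

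Reaching range is also part of the feasibility question, so removing ramps from the deviation count would hide something the trial is meant to measure. The textual contradiction and the treatment of zero hours survive all of this.

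**Conclusion.** The instruction for hypotension contradicts itself and must be reconciled; the documents do not settle which rule governs, and this review takes no view. The choice changes the mean delivered rate under either reading of SAP 4.2.1, in opposite directions. The liberal group shift of about 0.04 to 0.27 mL/kg/h rests on the assumed 6 h episode, slowed rate of 0.5, usual rates of 2.0 or 3.0, and 43% affected. It is not negligible beside 0.53, but it does not show that the criterion would be missed. The deviation difference depends on which exemption text applies. The ramp asymmetry is real in the limits (1.5 against 0) but conditional in its effect.

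**What to change.** 1. Reconcile item 11 of the Trial Summary, 7.4.1 item 8, Table 3 and 11.4 items iv and v into one instruction, the sponsor deciding which. Reconcile the 35 to 350 mL/h example in 7.2 at the same time.
2. In SAP 4.2.1, state one rule for zero-removal hours and report a sensitivity analysis under the other reading.
3. Use one hemodynamic exemption in 5.8.1, 10.1 and SAP 4.2.2, tied to the instability definition in 7.4.2.2. State whether the exemption for respiratory distress, absent from 10.1, stays.
4. Keep the deviation count as defined. As a supplement, report by arm the deviations that occur during protocol-required start or restart ramps, with time to range and the number who never reach range.

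The cost is wording and slightly more analysis. Initiation time, time to target, hourly rates, and hold reasons and durations are already collected (8.3.1, 8.3.2). An exemption wider than MAP will also exempt more hours than 10.1 does now, possibly more in the arm with more instability, so exempted episodes should be counted by arm.

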## 11.5 POTENTIAL BENEFITS

Study subjects may or may not receive any direct benefits from their participation in this study. Restrictive UFNET rates have been found to reduce risk of cardiac arrhythmias as well as short- and long-term mortality and KRT dependence in observational studies.

Restrictive UFNET rates may result in less hypotensive episodes and may result in overall net negative fluid balance and improved patient outcomes if risk of hypotension and subsequent fluid administration are reduced. The liberal UFNET rates may also result in overall reduced exposure to fluid overload, earlier liberation from mechanical ventilation and lower complications from fluid overload.

The knowledge gained from this study may be of significant benefit to future critically ill patients undergoing treatment with CKRT with a restrictive or liberal UFNET rate strategy. Understanding the UFNET rate-outcome relationship in acutely ill patients is critical for four reasons: a) to ensure that the provision of current care is safe, b) to design interventions to reduce mortality, c) to develop evidence-based clinical practice guidelines, and d) to implement quality measures during treatment with CKRT.

## 11.6 RISKS IN RELATION TO ANTICIPATED BENEFITS

Federal regulations at 45 CFR 46.111 (a)(2) require that “the risks to subjects are reasonable in relation to anticipated benefits, if any, to subjects, and the importance of the knowledge that may reasonably be expected to result.” Based on the preceding assessment of risks and potential benefits, the risks to subjects are reasonable in relation to anticipated benefits. Faster and slower UFNET rates are currently used in clinical practice. There is a potential for benefit to the society and individual patients should one of the UFNET strategies reduce complications and improve outcomes in a subsequent large phase III trial. Should one of the UFNET rate strategies, again consistent with clinical practice, prove to be harmful, the benefit will be in avoiding such therapies for future patients.

## 11.7 IMPORTANCE OF THE KNOWLEDGE TO BE GAINED

The knowledge gained from this trial will be used to design a large multicenter phase III trial to examine alternative UFNET rate strategies and its association with patient-centered clinical outcomes of 90-day mortality and dependence on KRT. We will also use the knowledge gained from this proposal to design other interventions to reduce the risks associated with UFNET. Such knowledge may serve to take precautionary measures to mitigate risks and prevent adverse events during UFNET in critically ill patients in the future.

This trial will also help us understand four key points, 1) whether it is feasible to maintain patients in the restrictive or liberal UFNET rates throughout the study; 2) an assessment of protocol adherence, 3) the patient recruitment rates in each center for the current trial, and 4) the effects of alternate UFNET rate strategies on patient's secondary clinical and safety outcomes. Thus, this study will enhance the scientific knowledge of understanding the UFNET rate-outcome relationship in critically ill patients.

